## Statistical Design and Power

**Brachial artery FMD.** FMD is expressed as the change in post-stimulus diameter as a percentage of the baseline diameter (FMD%). Our primary outcome is percent brachial flow-mediated dilation (FMD%). We employ a cross-over design since the most powerful test will compare the same subjects against themselves (i.e., avoiding many potential inherent subject differences). In a scenario with no anticipated differences, FMD correlations were observed to be 0.8 at 12 weeks (95% CI: 0.72, 0.87). Therefore, assuming an auto-regressive structure, we assume the correlation would be 0.64 at 26 weeks and 0.41 at 52 weeks. For a 25% relative difference (2% absolute difference) in FMD with 90%

Difference between groups	Power (alpha 0.05)	N	N plus 25% dropout
0.010	0.90	114	143
	0.80	86	108
0.015	0.90	52	65
	0.80	40	50
0.020	0.90	30	38
	0.80	23	29

power and alpha 0.05, we would need just 30 subjects (comparing singing interventions to sham/control). But, to compare the singing interventions to each other, using a delta of 0.015, we will need 52 subjects for 90% power and alpha 0.05. To have 52 evaluable subjects (assuming a 25% dropout rate), we will enroll 65 subjects. Please refer to the sample size table (shown above). We will be powered for all primary (FMD) and secondary outcomes (PAT and HRV). All outcome variables over 3 visits will be compared using analysis of variance (ANOVA) with repeated measures. The exposure variable is the singing (or sham) interventions.

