**PAT measurements.** *EndoPAT* is the FDA-cleared non-invasive test and device that provides an index of endothelial function in two forms: reactive hyperemia index (RHI) and LnRHI. The RHI is the post-to-pre-occlusion PAT signal ratio in the occluded side, normalized to the control side and further corrected for baseline vascular tone. Normal values for RHI are  $>1.67$ . In our small, pilot study, the average baseline RHI for 23 subjects was  $1.93 \pm 0.13$  (range: 0.93 to 3.62). There was a trend toward improvement to  $2.06 \pm 0.15$  – though we were underpowered for statistical significance. The LnRHI provides a better double-sided distribution than RHI that is closer to normal distribution. It offers better separation between disease states. The PAT ratio is the natural logarithm of the ratio of the post-deflation to baseline pulse amplitude in the hyperemic finger divided by the same ratio in the contralateral (control) finger. This ratio is based on the 90- to 120-second post-deflation interval, which had the strongest correlation to cardiovascular risk factors in the Framingham Heart Study cohort. We saw a significant improvement in the PAT ratio in our 23 subjects. We aim to confirm this finding with this study proposal, which is appropriately powered for both RHI and the PAT ratio.

We were unable to locate the reliable figures for within subject correlation measures of either the RHI or the PAT ratio in order to compute their power in a cross-over design. Fortunately, due to the size of the changes anticipated, sample size calculations for simple comparisons yield values similar to those planned. For example, given a change of 0.08 with 0.1 standard deviation in RHI, a sample size of 52 would yield a power of 81% with alpha 0.05. Therefore, in a cross-over design, we would be able to detect a change of 0.08 with power greater than 81% or we would be able to detect changes less than 0.08 with power equal to 81%. Similar remarks can be made for the PAT ratio.

**HRV measurements.** The normal-to-normal (NN) intervals include all intervals between adjacent ECG QRS complexes resulting from sinus node depolarizations. Standard measures of HRV (time domain analysis) include the standard deviation of all NN intervals (SDNN), the square root of the mean of the sum of the squares of differences between adjacent NN intervals (RMSSD), the natural log (ln)RMSSD and HRV score.

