For RMSSD, we also do not have reliable correlation numbers. However, for a simple comparison with a change of 15 and a standard deviation of 22.5 (based on our preliminary data), we would arrive at 65% power with a sample size of 52. Therefore, in a cross-over design, we would obtain more power and/or be able to detect smaller differences.

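### The SAP prefers LnRHI and lists lnRMSSD, but powers only raw RHI and raw RMSSD and names no analysis scale for its ANOVA

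*SAP*

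**What the plan says.** All of this is in the SAP under Statistical Design and Power.

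- **Method.** "All outcome variables over 3 visits will be compared using analysis of variance (ANOVA) with repeated measures". The text available for this review states no transformation, normality check or non-parametric fallback.
- **RHI.** The PAT paragraphs describe RHI and LnRHI and say of the second: "The LnRHI provides a better double-sided distribution than RHI that is closer to normal distribution". They add that it separates disease states better. The power example is nevertheless on the raw index: "given a change of 0.08 with 0.1 standard deviation in RHI", "a sample size of 52 would yield a power of 81% with alpha 0.05". LnRHI has no power figure and is not named as the analysed form.
- **PAT ratio.** It is defined as a natural logarithm, so it is already on the log scale.
- **HRV.** The listed measures are SDNN, RMSSD, "the natural log (ln)RMSSD and HRV score". Power is given for RMSSD only, in raw units (change 15, SD 22.5): "we would arrive at 65% power with a sample size of 52".
- **Sample size.** "To have 52 evaluable subjects (assuming a 25% dropout rate), we will enroll 65 subjects".

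The protocol synopsis adds salivary cortisol and cytokines, measured before and after each intervention under the exploratory Aim 3. It gives no mean, spread or scale for them.

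**The concern.** The SAP gives its own reason to work with the log of RHI and does not act on it. A reader cannot tell whether the secondary PAT and HRV analyses will use RHI or LnRHI, RMSSD or lnRMSSD.

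Two things are at stake. If a measure is right-skewed and singing acts proportionally, a few high values inflate the variance of raw differences and power falls. Separately, when two forms of one measure are available and neither is named as the lead, the choice can be made after the results are seen.

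The same ANOVA sentence would cover cortisol and cytokines, for which skew would matter more if it is present. The primary outcome, FMD%, is not affected.

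**Working it through.** **1. Reproducing the stated power.** Unpaired two-sample t test, two-sided alpha 0.05 (the SAP does not state sidedness), 52 subjects in total, so 26 per group. Noncentrality = d × √(26/2).

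| Measure | d = change / SD | Noncentrality | Power | SAP |
|---|---|---|---|---|
| RHI | 0.08 / 0.1 = 0.80 | 2.88 | 80.7% | 81% |
| RMSSD | 15 / 22.5 = 0.667 | 2.40 | 65.4% | 65% |

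With 52 per group the figures would be 98% and 92%, and for a paired test with the SD read as that of the differences over 99%. Neither matches. Both stated figures are therefore raw-unit, unpaired calculations with the SD used as a between-subject SD.

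**2. What the pilot says about skew.** RHI mean 1.93, range 0.93 to 3.62, n = 23.

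- Raw scale: 1.93 − 0.93 = 1.00 below the mean, 3.62 − 1.93 = 1.69 above.
- Log scale: ln 0.93 = −0.07, ln 1.93 = 0.66, ln 3.62 = 1.29, so 0.73 below and 0.63 above.

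This agrees with the SAP's remark on LnRHI but rests on two extreme values.

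**3. The RHI SD.** The pilot figure is 1.93 ± 0.13, with ± undefined. The smallest sample SD that 23 values with this mean and range can have is found by placing the other 21 at one point: (23 × 1.93 − 0.93 − 3.62)/21 = 1.897. Then SD = √[(1.00² + 1.69² + 21 × 0.033²)/22] = √(3.879/22) = 0.42. So 0.13 cannot be the SD. Read as a standard error, SD = 0.13 × √23 = 0.62, CV = 0.62/1.93 = 0.32, and log-SD = √ln(1 + 0.32²) = 0.315. An SD of 0.1 does not fit the pilot as a between-subject SD.

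**4. Raw against log for RHI.** Simulated paired contrast, n = 52, lognormal data (assumption), t test on raw and on log differences.

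| Log-SD | Rise | Correlation (assumed) | Raw | Log |
|---|---|---|---|---|
| 0.315 | 10% | 0.4 | 47% | 50% |
| 0.315 | 10% | 0.6 | 63% | 66% |
| 0.315 | 10% | 0.8 | 90% | 92% |
| 0.315 | 5% | 0.6 | 22% | 23% |
| 0.052 (SAP's SD 0.1) | 2% | 0.6 | 86% | 86% |

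Across correlations 0.4 to 0.8 and rises of 5 to 10%, the log scale gains about 1 to 4 points. At the SAP's SD of 0.1 it gains nothing.

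**5. RMSSD.** The SAP gives a change and an SD but no mean, so no CV or log-SD can be derived and no loss can be computed.

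**6. Cortisol and cytokines.** Every input is assumed: lognormal data, 35% rise, correlation 0.6, n = 52.

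| Assumed log-SD | Raw | Log | Difference |
|---|---|---|---|
| 0.6 | 93% | 98% | 5 points |
| 0.8 | 66% | 84% | 18 points |
| 1.0 | 40% | 66% | 26 points |

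In related runs (CV 0.05 to 1.5, correlation 0.3 to 0.8) the raw-scale type I error stayed at about 5% or below.

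**7. RHI power restated on the log scale.** A change of 0.08 from 1.93 is ln(2.01/1.93) = 0.0406. SD of the log difference = 0.315 × √(2(1 − ρ)), which is 0.315, 0.199 and 0.141 at an assumed ρ of 0.5, 0.8 and 0.9. Paired power at n = 52 is about 15%, 30% and 53%. The RHI power claim thus depends far more on the SD than on the scale.

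**The case against.** The SAP never says untransformed. It lists LnRHI and lnRMSSD among its measures, and a repeated-measures ANOVA can be run on either. A log-scale PAT outcome is already planned: the PAT ratio is a logarithm, it is the measure that improved significantly in the pilot, and the SAP sets out to confirm that result. The only loss that can be tied to document figures is a few points for RHI. The lognormal model builds in the advantage of logs. The evidence of skew is thin: in normal samples of 23, an upper-to-lower distance ratio of 1.69 or more arises about 4% of the time (about 9% in either direction). A crossover analysis also depends on within-subject differences, not on the baseline spread. Type I error is not inflated.

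All of this stands as a limit on size. It rules out a reading that a reader might infer, namely that the SAP has chosen raw-scale analysis and so loses material power. It does not remove the gap: RHI and RMSSD each appear in two forms, the only powered form is the raw one, and neither is named for analysis. SDNN and the HRV score are different measures rather than scales of RMSSD, so choosing among them is a separate question.

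**Conclusion.** A minor point that holds. The analysis scale for RHI and RMSSD is unspecified, and their power is given on the scale that the SAP's own reasoning does not favour for RHI. If raw values were used, RHI would lose about 1 to 4 power points, assuming lognormal data and reading ±0.13 as a standard error (SD about 0.62). At SD 0.1 it would lose nothing. The RMSSD loss cannot be computed.

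A reader might infer that cortisol and cytokine analyses are seriously underpowered. The documents do not support that. They give no distribution for these markers, and the 5 to 26 points follow entirely from the assumed log-SD of 0.6 to 1.0, rise of 35% and correlation of 0.6. Part of the SAP was also not available for this review and may deal with them.

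The RHI SD of 0.1 is the larger weakness in the RHI power statement. A change of scale does not cure it, but restating power on the log scale would bring it into the open.

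**What to change.** Add to the SAP:

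- LnRHI and lnRMSSD are the analysed forms of RHI and RMSSD. Raw RHI and RMSSD are reported descriptively.
- The PAT ratio is analysed as defined, since it is already a logarithm.
- Salivary cortisol and each cytokine are log-transformed.
- For log-transformed variables, contrasts between conditions are back-transformed and reported as geometric mean ratios with confidence intervals.

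Restate RHI and RMSSD power on the log scale for the paired design. For RHI, use an SD that fits the pilot range of 0.93 to 3.62, and show a range of within-subject correlations, since the SAP says it has no reliable figure. For RMSSD, take the log-scale SD from the preliminary data, because the documents do not give the mean needed to derive it.

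The cost is SAP wording and one recalculation, with no new data, visits or participants. The downside is that results read as ratios rather than raw differences. The restated RHI power may also fall well below 81%, which would come from the SD and not from the log scale.

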The research team member will assist the subject in completing the study questionnaire, including demographics, medical history, current medications, current exercise and singing habits and physical limitations and/or mobility issues. A target heart rate (60% of 220-age) will be calculated. The subject will be educated on the BORG Rating of Perceived Exertion and target heart rate goals for singing. A visual analog mood score (ArtsObs) will be obtained prior to singing (or sham) intervention. Baseline salivary samples will be obtained (for cortisol and cytokines). The subject will be moved to a seated position for the singing intervention.

Subjects will undergo the following three interventions (separate Visits 1-3) in a cross-over design, separated by a minimum of 2 days (to allow for wash-out effects of the prior intervention):

1. Singing intervention 1 (instructional sing-a-long video): A video series will be created and recorded for the purposes of the study. The videos will include a vocal warm-up (10 minutes long). The subject will then have the option to select and sing two songs (10 minutes each), with offerings in four music genres including Folk, Pop, Country, and a Hymn. Each piece will vary in tempo, melodic contour, and rhythm. The total duration of singing via this format will be 30 minutes. The videos will be led by [name], Associate Professor of Voice and Voice Area Head at the University of Wisconsin-Milwaukee, with an inexperienced, older singer participating in the music making.
2. Singing intervention 2 (in-person music therapy session): Intake forms will be distributed to participants prior to starting music therapy for these sessions. These forms are used

to assess musical preference, prior music experiences as well as any medical conditions to take into consideration. Music therapy sessions will begin with vocal and breathing warm-up exercises for about 10 minutes. Upon completion of these exercises, subjects will choose a preferred song to sing from the multi-genre binder that the music therapist (MT) created specifically for this research based on age and preferences of patients.

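### The 81% power for an RHI change of 0.08 assumes an SD of 0.1, but the pilot range in the same SAP section forces a pilot SD of at least 0.42

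*SAP*

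**What the plan says.** All the power material is in the SAP, Statistical Design and Power. Under PAT measurements, the pilot baseline RHI in 23 subjects is given as 1.93 ± 0.13 ("range: 0.93 to 3.62). There was a trend toward improvement to" 2.06 ± 0.15), and the change is described as not reaching significance. The ± figures are not labelled as SD or standard error.

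The SAP then admits a gap: "We were unable to locate the reliable figures for within subject correlation measures of either the RHI or the PAT ratio". It falls back on a simple comparison: "given a change of 0.08 with 0.1 standard deviation in RHI, a sample size of 52 would yield a power of 81" per cent at alpha 0.05. No source is given for the SD of 0.1. From this it concludes that "in a cross-over design, we would be able to detect a change of 0.08 with power greater than 81" per cent. The PAT ratio is covered by one sentence: "Similar remarks can be made for the PAT ratio".

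Two general statements depend on this. Under PAT measurements, the study is one "which is appropriately powered for both RHI and the PAT ratio". Under Brachial artery FMD: "We will be powered for all primary (FMD) and secondary outcomes (PAT and HRV").

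**The concern.** An SD of 0.1 does not fit the spread printed a few lines earlier. Baseline values from 0.93 to 3.62 in 23 people span 2.69 units, about 27 times the assumed SD. If 0.1 is too small, the 81% is too high, and it cannot serve as a floor for the crossover.

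This is the only power calculation given for RHI. A null RHI result would be read against a claimed power above 81%, and could be taken as evidence of no effect when the study may have had little chance of detecting a change of that size.

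**Working it through.** **Inputs (SAP, Statistical Design and Power).** Change 0.08; SD 0.1; N = 52; alpha 0.05 (two-sided assumed, as the SAP does not say). Pilot n = 23, mean 1.93, minimum 0.93, maximum 3.62, ± 0.13. Powers below use the noncentral t distribution.

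**1. Reproduce the 81%.**

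| Reading | Power |
|---|---|
| 26 v 26, SD 0.1 (standardised difference 0.8) | 80.7% |
| 52 v 52, SD 0.1 | 98.1% |
| 52 pairs, SD of differences 0.1 | over 99.9% |

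Only the first matches. The SAP's RMSSD example (change 15, SD 22.5, N = 52, stated 65%) reproduces the same way: 26 v 26 gives 65.4%. So 0.1 is used as the between-subject SD of RHI in a two-group comparison. The arithmetic is right; the SD is the problem.

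**2. Smallest SD the pilot figures allow.** Put one value at each extreme and set the other 21 equal, keeping the mean at 1.93. The extremes deviate by −1.00 and +1.69, so the other 21 deviations sum to −0.69:

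SD_min = √[(1.00² + 1.69² + 0.69²/21) / 22] = √[(1.000 + 2.856 + 0.023) / 22] = 0.42

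Rounding of the inputs moves this only between 0.418 and 0.422. No distributional assumption is involved. Neither 0.1 nor 0.13 can be the pilot SD.

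**3. Likely pilot SD.** If ± 0.13 is a standard error, SD = 0.13 × √23 = 0.62 (normal-theory 95% interval 0.48 to 0.88).

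**4. The SAP's own calculation with these SDs.** 26 v 26, change 0.08: about 10% at SD 0.42 and 7% at SD 0.62, against 81% stated.

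**5. The crossover, which is the actual design.** With 52 pairs, SD of differences = SD × √[2(1 − ρ)]. The SAP gives no ρ for RHI, so all values are assumptions. The calculation takes one RHI value per visit with equal SDs and no baseline adjustment.

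| Assumed ρ | Power for 0.08, SD 0.42 | Power for 0.08, SD 0.62 | Detectable at 80% power, SD 0.42 | Detectable at 80% power, SD 0.62 |
|---|---|---|---|---|
| 0.3 | 21% | 12% | 0.20 | 0.29 |
| 0.5 | 27% | 15% | 0.17 | 0.25 |
| 0.8 | 57% | 30% | 0.11 | 0.16 |
| 0.9 | 85% | 53% | 0.07 | 0.11 |
| 0.95 | 99% | 82% | – | – |

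Power of 81% for 0.08 needs an SD of differences of about 0.20. The correlation required is 1 − 0.20²/(2 × SD²): about 0.89 at SD 0.42 and 0.95 at SD 0.62.

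**6. A larger change.** For 0.13, the change seen in the pilot (2.06 − 1.93), 52 pairs at SD 0.62 give 31%, 65% and 91% at ρ = 0.5, 0.8 and 0.9. At SD 0.42, power is 93% at ρ = 0.8 and over 99% at ρ = 0.9.

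**The case against.** The strongest objection is that the pilot range describes baseline values, so it bounds the SD of baseline RHI only. If 0.1 were the SD of pre-to-post change scores, a 26 v 26 comparison of those changes would also give 80.7%. This reading fails on two counts. The SAP calls it an SD in RHI. And with a change SD of 0.1, the pilot change of 0.13 in 23 subjects would have given t = 0.13/(0.1/√23) = 6.2, not an underpowered trend. If the pilot test was paired and two-sided at 5% (an assumption), non-significance implies a change SD of at least 0.13 × √23 / 2.07 = 0.30. At that SD, 52 pairs have about 47% power or less for 0.08.

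Second, the SAP never says that 0.1 came from the pilot, and the Protocol's Brief Summary promises a more targeted population. A pilot sample cannot strictly exclude a smaller SD in the trial. That is fair, but the documents offer no data for an SD less than a quarter of the pilot minimum.

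Third, 10% and 7% belong to a parallel comparison that the trial will not run. This stands: they show what happens to the SAP's own figure. The crossover figures are the relevant ones, and at SD 0.42 with a correlation of 0.9 they exceed 81%. The crossover claim is therefore unsupported, not disproved.

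Finally, 0.08 is offered as an example and RHI is secondary. Both are true and limit the weight of the point, but no other RHI calculation is given.

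**Conclusion.** The concern holds. The SD of 0.1 behind the 81% is unsourced and incompatible with the pilot spread in the same section, where the SD is at least 0.42 and about 0.62 if ± 0.13 is a standard error. For an RHI change of 0.08, neither 81% nor a higher crossover figure is supported. Crossover power is 15% to 53% at SD 0.62 and 27% to 85% at SD 0.42, for assumed correlations of 0.5 to 0.9.

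The finding is confined to a change of 0.08 and relies on the pilot spread as a guide to the trial. The PAT ratio is not shown to be underpowered: its pilot improvement was significant, but its power is argued only by analogy. The FMD-based numbers do not depend on this calculation. This should be fixed, but it does not threaten the primary analysis.

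**What to change.** - Label the pilot ± values as SD or standard error.
- Replace 0.1 with the pilot SD and recompute for the paired design over a stated range of correlations. The pilot pre/post correlation is only a guide: it is same-session, whereas the trial visits are (Protocol, Study Design Narrative) "in a cross-over design, separated by a minimum of 2 days".
- Report the detectable RHI difference under those assumptions. The table above is illustrative and should be redone from the pilot data.
- Delete the 81% and the inference that the crossover exceeds it.
- Narrow the two general power statements so that they do not cover an RHI change of 0.08.
- Support the PAT-ratio claim with that measure's own pilot data.

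The cost is one recalculation from data the sponsor holds and some SAP wording. The stated RHI power becomes less favourable. No extra participants are needed, and 52 evaluable and 65 enrolled stay as they are.
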